8.1 Efficacy Assessments

Patients will have their tumors assessed for response by conventional imaging methods (typically CT scans), which will be performed at baseline (at least 30 days prior to the first study drug dose) and then at least every 2 cycles (~ every 6 weeks) after initial dose. Once patients have completed 4 cycles of therapy, they can have CT scans after every 3 cycles.

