7.1 Screening Visit

The screening visit will occur up to 30 days prior to initiating study treatment.

- Medical History - SGC diagnosis, prior SGC treatment history, and demographics.
- Physical examination - examination of major organ systems, ECOG performance status, body weight and vital signs (i.e., blood pressure, heart rate).
- Laboratory Evaluations will be obtained up to 14 days prior the first dose of eribulin
 - Hematology (CBC with platelets and absolute neutrophil count)
 - Blood chemistry (sodium, potassium, chloride, carbon dioxide, creatinine, BUN, glucose, calcium, LDH, albumin, bilirubin, AST, ALT, total protein, alkaline phosphatase, magnesium)

- Pregnancy test - serum or urine pregnancy test performed for all women of childbearing potential
- CT scan for known sites of involvement.
- ECG If < 450, no further monitoring. If > 450, needs ECG prior to second dose of eribulin. If > 480, eribulin needs to be held until QTc value is within protocol specified range.

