7.5 Subject Withdrawal

Patients will be removed from study if they present with disease progression, as defined by radiological RECIST 1.1 criteria. Subjects will also be removed from study if they require more than two dose level reductions. Subjects will also be removed from study if they require more than 3 weeks to recover from adverse events. Patients may withdraw consent at any time.

8. Assessments

The schedule of assessments is presented in Appendix 1. The description of assessments is provided in Section 7.

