8.1.2 Baseline Documentation of Tumor Burden

- Target lesions: All measurable lesions should be identified and recorded and measured at baseline. Target lesions should be selected on the basis of their size (those with the longest diameter) and their suitability for accurate repeated measurements (either by imaging techniques or clinically). A sum of the longest diameter for all target lesions will be calculated and reported as the baseline sum longest diameter (SLD). The baseline SLD will be used as the reference by which to characterize the objective tumor response.
- Non-target lesions: All other lesions (or sites of disease) should be identified as non-target lesions and should also be recorded at baseline. Measurements of these lesions are not required, but the presence or absence of each should be noted throughout follow-up.

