8.1.3 Response Criteria

Radiological response will be defined as per the RECIST criteria. Treatment outcomes will be defined as:

- Complete response (CR): complete resolution of all tumor lesions.
- Partial response (PR): at least a 30% decrease in the sum of the longest diameter of the target lesions (primary tumor and lymph nodes).
- Stable disease (SD): patients with changes that would not qualify as partial responses or progressive diseases.
- Progressive disease (PD): at least a 20% increase in the sum of the longest diameter of the target lesions.

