Appendix 1. Schedule of Assessments

Procedure	Screening		Every 21 days		End of tmt	30 day post ⁵ tmt
	within 30 days	within 7 days	Day 1	Day 8		
Physical Exam	X		X	X	X	X
Medical History	X					
Pregnancy Test		X				
Hematology ¹	X		X	X	X	X
Serum Chemistries ²	X		X	X	X	X
EGG	X	X ⁴				
CT scans ³	X		X		X	
Eribulin			X	X		
AE Assessment			X	X	X	X

¹ Serum chemistries include sodium, potassium, chloride, carbon dioxide, creatinine, BUN, glucose, calcium, LDH, albumin, bilirubin, AST, ALT, total protein, alkaline phosphatase, magnesium.

² CBC with platelets and absolute neutrophil count.

³ CT scan for known sites of involvement after every 2 cycles of combined therapy. After 4 cycles of therapy scans may be repeated after every 3 cycles.

⁴ If > 450, needs ECG prior to second dose of eribulin.

⁵ 30 day follow-ups can be done at patients' local physician

13. References

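### Section 8.1 makes 30 days the minimum age of the baseline tumour scan, while Section 7.1 and Appendix 1 make it the maximum; the three rules agree only on Day -30

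*Combined protocol and SAP*

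**What the plan says.** Three places in the combined protocol and SAP set the timing of the baseline scan.

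- Section 8.1 (Efficacy Assessments): imaging is "performed at baseline (at least 30 days prior to the first study drug dose".
- Section 7.1 (Screening Visit): "The screening visit will occur up to 30 days prior to initiating study treatment". The components of that visit include "CT scan for known sites of involvement" as a separate bullet, outside the 14-day limit that applies to the laboratory tests.
- Appendix 1 (Schedule of Assessments): the screening CT is marked in the column headed "within 30 days".

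Section 8 opens with a pointer to the other two places: "The schedule of assessments is presented in Appendix 1. The description of assessments is provided in Section 7".

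Section 8.1.2 gives the scan its role: "The baseline SLD will be used as the reference by which to characterize the objective tumor response". Section 8.1.3 defines partial response (PR) as "at least a 30% decrease in the sum of the longest diameter of the target lesions" and progressive disease (PD) as "at least a 20% increase in the sum of the longest diameter of the target lesions". Under Section 10.2 response rate is the primary endpoint, and time to progression is summarised as a median.

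**The concern.** Section 8.1 turns an upper limit into a lower one. Taken literally, a CT one week before first dose breaches it and a CT three months before first dose complies.

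The baseline sum of longest diameters (SLD) is the denominator for every later response call. If target lesions grow between an old scan and the first dose, the baseline SLD understates the tumour burden when treatment starts. Part of any later shrinkage then only offsets that growth, so PR is harder to reach, and part of the 20% increase that defines PD has been used up before treatment. Both effects run against the drug: response rate is biased downward and time to progression is shortened.

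The decision rule in Section 10.1 turns on few responders (none among the first 10 stops the trial, and 4 of 29 is the threshold for success), so the reference measurement should be defined without ambiguity.

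**Working it through.** **1. Overlap of the windows.** Let d be the number of days from scan to first dose.

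- Section 8.1: d ≥ 30.
- Section 7.1: d ≤ 30, which the CT inherits as a listed part of the screening visit.
- Appendix 1: d ≤ 30.

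The intersection is d = 30 alone. Day -30 to Day -1 is 30 days, of which 30 − 1 = 29 satisfy Section 7.1 and Appendix 1 but breach Section 8.1. If the dosing day is counted as well, the figure is 30 of 31.

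**2. The plan's own figures.** No stated figure depends on the scan window. As a background check, the Simon design in Section 10.1 reproduces. The probability of stopping early under the null is 0.95^10 = 0.599 (stated 0.60). The expected sample size is 10 + (1 − 0.5987) × 19 = 17.6 (stated 17.6). Exact type I error is 0.0468 and exact power 0.801. This point leaves all of these unchanged.

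**3. What an older scan could do (illustration only).** The growth rates and the Day -60 and Day -90 scan ages are assumed. Section 5.1 requires progression within 6 months of entry, but new lesions or clinical deterioration also qualify, and it gives no interval over which a 20% increase accrued. It therefore yields no growth rate.

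Assume constant exponential growth of 20% per T months of 30 days. Growth from scan to first dose is

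G(d) = 1.2^(d/(30T)), with G = 1 if there is no growth.

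If S is the SLD on the day of first dose, the baseline SLD is S/G. Then:

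- PR requires shrinkage from S of 1 − 0.70/G.
- PD is reached after growth from S of 1.20/G − 1. This takes the baseline SLD as the reference for PD, since Section 8.1.3 names no other.

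Worked case, T = 3 and d = 60: G = 1.2^(60/90) = 1.129. PR requires 1 − 0.70/1.129 = 38.0%, and PD is reached at 1.20/1.129 − 1 = 6.3%.

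| Assumed growth | G at Day -30 / -60 / -90 | Shrinkage needed for PR | Growth that reaches PD |
|---|---|---|---|
| None | 1 / 1 / 1 | 30.0% / 30.0% / 30.0% | 20% / 20% / 20% |
| 20% per 12 months | 1.015 / 1.031 / 1.047 | 31.1% / 32.1% / 33.1% | 18.2% / 16.4% / 14.7% |
| 20% per 6 months | 1.031 / 1.063 / 1.095 | 32.1% / 34.1% / 36.1% | 16.4% / 12.9% / 9.5% |
| 20% per 3 months | 1.063 / 1.129 / 1.200 | 34.1% / 38.0% / 41.7% | 12.9% / 6.3% / 0% |

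The last PD entry is 0 by construction, because 20% growth over 90 days uses up the whole PD margin.

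**4. The part due to the wording.** A Day -30 scan remains allowed after correction, so it is the right comparator. Differences from Day -30, in percentage points and from unrounded values:

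| Assumed growth | Extra shrinkage for PR, Day -60 / -90 | PD margin lost, Day -60 / -90 |
|---|---|---|
| None | 0 / 0 | 0 / 0 |
| 20% per 12 months | 1.0 / 2.1 | 1.8 / 3.5 |
| 20% per 6 months | 2.0 / 4.0 | 3.5 / 6.9 |
| 20% per 3 months | 3.9 / 7.5 | 6.7 / 12.9 |

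**The case against.** The strongest reply is that this is an editorial slip with little practical reach. Section 8 defers to Appendix 1 and Section 7 for the schedule, and both give a 30-day maximum. A Day -60 or Day -90 scan would breach both, so the bias arises only if staff follow one parenthesis against the visit description and the schedule, in a single-center trial (Section 4). Staff who satisfy all three texts scan on Day -30, and staff who follow the schedule scan on Day -30 or later; measured against a Day -30 scan, neither group has any extra bias. The growth rates are assumed, and their range begins at zero. Time to progression is descriptive, and a bias against the drug would not create a false positive.

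Most of this stands, and it limits the practical risk. The cross-reference shows the likely intent, but it does not withdraw the contrary rule, which sits in the efficacy section and is specific to tumour imaging. Anyone checking compliance against Section 8.1 would record a deviation for a scan done on schedule and none for an outdated one. A bias against the drug is also not harmless in a trial meant to screen for activity, since it can cost a responder.

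Two limits on the evidence deserve mention. Section 7.1 states its limit for the visit as a whole, and the Appendix 1 column is read from a table extracted from PDF. The prose of Section 7.1 establishes the conflict without the table.

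**Conclusion.** The concern holds. The contradiction is certain on the text, and nothing in the documents resolves it. It affects the reference measurement for the primary endpoint and should be corrected, although the expected harm is modest because the schedule staff are most likely to use is sound.

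The direction of any bias is clear if lesions grow before first dose. Its size is unknown, since it depends on growth rates and actual scan ages that the documents do not give, and it is zero if scans follow Section 7.1 and Appendix 1. No effect on the design's stated type I error or power is claimed.

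**What to change.** In Section 8.1, reword the parenthesis so that baseline imaging takes place no more than 30 days before the first dose of study drug. Sections 8.1 and 7.1 and Appendix 1 then state one window.

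The cost is one phrase in the protocol. There is no operational cost, because Section 7.1 and Appendix 1 already plan the scan within that window.

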8.1.1 Definition of Measurable Disease

Measurable disease: the presence of at least one lesion that can be accurately measured in at least one dimension (longest diameter to be recorded) as ≥ 10 mm with spiral CT scan for non-lymph nodes or ≥ 1.5 cm in short-axis diameter for lymph nodes

Non-measurable disease: all other lesions, including small lesions (longest diameter < 10 mm with spiral CT scan).

8.1.2 Baseline Documentation of Tumor Burden

- Target lesions: All measurable lesions should be identified and recorded and measured at baseline. Target lesions should be selected on the basis of their size (those with the longest diameter) and their suitability for accurate repeated measurements (either by imaging techniques or clinically). A sum of the longest diameter for all target lesions will be calculated and reported as the baseline sum longest diameter (SLD). The baseline SLD will be used as the reference by which to characterize the objective tumor response.
- Non-target lesions: All other lesions (or sites of disease) should be identified as non-target lesions and should also be recorded at baseline. Measurements of these lesions are not required, but the presence or absence of each should be noted throughout follow-up.

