5.1 Inclusion Criteria

Patients are eligible to be included in the study only if they meet all of the following criteria:

- Patients must have histologically or cytologically documented salivary gland cancers. Patients that do not have a salivary gland primary must have one of the following histologies - adenoid cystic carcinoma, mucoepidermoid carcinoma, acinic cell carcinoma).
- Patients must have recurrent and/or metastatic disease that is progressive and not amenable to surgery or curative radiotherapy occurring within 6 months of study entry, as evidenced by: at least a 20% increase in radiographically or clinically measurable disease, appearance of any new lesions, or deterioration in clinical status.
- Age \geq 18 years.
- ECOG performance status of 0, 1, or 2.
- Patients with measurable disease per RECIST 1.1 criteria [Eisenhauer].
 - At least one lesion of \geq 1.5 cm in long-axis diameter for nonlymph nodes or \geq 1.5 cm in short-axis diameter for lymph nodes which is serially measurable according to RECIST 1.1 using either computerized tomography (CT) or magnetic resonance imaging (MRI).
 - Lesions that have had radiotherapy must show evidence of progressive disease (PD) based on RECIST 1.1 to be deemed a target lesion.
- Patients must have normal organ and marrow function as defined below:
 - absolute neutrophil count \geq 1,500/ μ L
 - platelets \geq 100,000/ μ L
 - creatinine clearance \geq 40 mL/min
 - bilirubin \leq 1.5 ULN
 - Alkaline phosphatase \leq 3 ULN. If total ALP is $>$ 3 x ULN (in the absence of liver metastasis) or $>$ 5 x ULN in subjects with liver metastasis AND the subject is known to have bone metastases, then liver ALP iso-enzyme should be used to assess liver function rather than total ALP.
 - AST and ALT \leq 3 X ULN,
- Women of child-bearing potential (WOCP) and men must agree to use adequate contraception (hormonal or barrier method of birth control or abstinence) prior to study entry and for the duration of study participation.
- Life expectancy of $>$ 12 weeks.
- Signed and dated informed consent document indicating that the patient has been informed of all the pertinent aspects of the trial prior to enrollment.

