10.1 Sample Size Determination

This is an open-label single-arm phase II study. We will utilize the optimal two-stage Simon design, which minimizes the expected number of patients enrolled under the null hypothesis and given various other assumptions [Simon]. The null hypothesis is that the true response rate is 5% and the alternative hypothesis is that the true response rate is 20%. If we additionally set the significance level to 0.05 (or less) and the power to be at least 80% ($p_0 = 0.05$, $p_1 = 0.20$, $a = 0.05$, $b = 0.20$), then Simon's design dictates that 10 subjects be treated in the first stage. If there are no responses among these 10, the study will be terminated due to lack of efficacy (i.e., this will be considered reasonably strong evidence against the alternative hypothesis that the response rate is 20% or more). If at least one response is observed among these 10, an additional 19 subjects will be recruited for a total of 29 subjects. If 3 or fewer responses are seen among the 29 (an observed response rate of 10.3% or less), the regimen will be deemed to be not sufficiently efficacious for further study. Four or more responses among the 29 will be viewed as sufficient evidence to deem the regimen as potentially efficacious (i.e., reasonably strong evidence that the true response rate is greater than 5%). The expected number of patients to be enrolled under the null hypothesis that the true response rate is 5% is 17.6, and the probability of terminating early in this scenario (after the first stage, i.e., if no responses are seen in the first 10 patients) is 0.60.

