10.2 Efficacy Analysis

The primary endpoint will be overall response rate. As noted above, 4 or more observed responses among 29 patients would be considered potentially efficacious and would justify further study. Responses include both complete and partial responses, as defined by RECIST 1.1 criteria. Duration of response and time to progression will be reported as median values. The disease control rate (DCR), defined as the stable disease + partial response rate will be calculated. Toxicity rates will be described as the overall percentage of patients experiencing Grade 3 or higher toxicity.

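### Sections 8.1.2 and 8.1.3 do not define one lesion sum for the primary endpoint: partial response and progression are worded over different lesion sets, the axis for nodal targets is unsettled, and no text says whether RECIST 1.1 governs

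*Combined protocol and SAP*

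**What the plan says.** **Which lesions.** Section 8.1.2 takes target lesions from all measurable lesions, with no limit by site: "A sum of the longest diameter for all target lesions will be calculated and reported as the baseline sum longest diameter (SLD". That baseline sum is the reference for response. Section 8.1.3 then defines PR as "at least a 30% decrease in the sum of the longest diameter of the target lesions (primary tumor and lymph nodes", closing the parenthesis there. The progression line in the same list uses the sum over target lesions with no parenthesis. The complete response line refers to all tumor lesions. Section 5.1 admits recurrent and/or metastatic disease.

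**Which axis.** Section 5.1 admits a node of at least "1.5 cm in short-axis diameter for lymph nodes which is serially measurable according to RECIST 1.1", and 8.1.1 repeats the threshold as "1.5 cm in short-axis diameter for lymph nodes". Sections 8.1.2 and 8.1.3 use longest diameter for every target, with no exception for nodes.

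**Which standard.** Section 8.1.3 opens by referring to RECIST without a version and then writes out its own definitions. Section 10.2 says "Responses include both complete and partial responses, as defined by RECIST 1.1 criteria". No section says what happens if the written-out definitions and the reference differ.

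**The concern.** Two readers who both follow the plan could score the same scans differently. One could take the PR sum over the primary and nodes, the other over all targets. One could measure a nodal target by longest diameter, as 8.1.2 says; the other could follow the axis on which it qualified, or the RECIST 1.1 reference.

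The literal reading of the PR line is the sharper problem. In a trial open to metastatic disease, a patient whose targets are all distant metastases would have no sum on which PR could be declared, so complete response would be the only way to count as a responder. A patient with both kinds of target would have one sum for PR and another for progression.

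The decision rests on very few events. On the first stage the plan says: "If there are no responses among these 10, the study will be terminated due to lack of efficacy". At the end, three responses of 29 is a failure and four is a success. One reclassified patient can change either decision.

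**Working it through.** **1. Reproduce the design (10.1).** Inputs: null rate 0.05, alternative 0.20, 10 patients in stage 1, stop at 0 responses, 29 in total, success at 4 or more. With p the rate at which patients are scored as responders,

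P(success | p) = Σ over x = 1 to 10 of C(10,x) pˣ(1−p)¹⁰⁻ˣ × P(Bin(19,p) ≥ max(0, 4−x)).

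- p = 0.05: type I error 0.0468.
- p = 0.20: power 0.8011.
- Early stop under the null: 0.95¹⁰ = 0.5987 (plan: 0.60).
- Expected size under the null: 10 + (1 − 0.5987) × 19 = 17.62 (plan: 17.6).

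The design reproduces. It meets both of its limits with little to spare, provided scored responses equal true responses.

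**2. Can the wording change a patient's category?** The measurements below are hypothetical (mm). PR needs a decrease of at least 30%.

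| Case | Sum A | Sum B |
|---|---|---|
| Primary 30→24, lung 40→24 | all targets 70→48: −31.4%, PR | primary only: −20.0%, not PR |
| Primary 40→26, lung 30→32 | all targets 70→58: −17.1%, not PR | primary only: −35.0%, PR |
| Node 18×30→11×24 | short axis: −38.9%, PR | longest diameter: −20.0%, not PR |
| Node 18×30→15×20 | short axis: −16.7%, not PR | longest diameter: −33.3%, PR |
| Lung 40→24, node 18×30→14×26 | node by short axis 58→38: −34.5%, PR | node by longest diameter 70→50: −28.6%, not PR |

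Both ambiguities can remove a PR or create one. The last row shows that the axis can still matter when a non-nodal target is in the sum.

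**3. Effect on the decision rule.** The documents give no misclassification rate, so the ranges are assumed. If a fraction q of true responders is missed, the scored rate is p(1−q). If a fraction f of non-responders is scored PR, it is p + (1−p)f.

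Missed responders, true rate 0.20:

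| q | Scored rate | Power | Chance of stopping at stage 1 |
|---|---|---|---|
| 0 | 0.20 | 0.801 | 0.107 |
| 5% | 0.19 | 0.768 | 0.122 |
| 10% | 0.18 | 0.730 | 0.137 |
| 20% | 0.16 | 0.641 | 0.175 |
| 30% | 0.14 | 0.534 | 0.221 |

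False PRs, true rate 0.05:

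| f | Scored rate | Type I error |
|---|---|---|
| 0 | 0.0500 | 0.047 |
| 1% | 0.0595 | 0.078 |
| 2% | 0.0690 | 0.118 |
| 3% | 0.0785 | 0.165 |
| 5% | 0.0975 | 0.274 |

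With q = 10% and f = 2% together, the scored rates are 0.05 × 0.9 + 0.95 × 0.02 = 0.064 and 0.20 × 0.9 + 0.80 × 0.02 = 0.196. Type I error is then 0.096 and power 0.788: power looks almost intact while the error rate has about doubled.

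**The case against.** The best defense is that 10.2 defines responses by RECIST 1.1, 8.1.3 opens with a reference to RECIST, and 5.1 ties measurability to RECIST 1.1. On that view 8.1.2 and 8.1.3 are a loose paraphrase and the cited standard decides. This would settle the matter if the plan said so. It does not: 8.1.3 gives its own definitions, 8.1.2 makes its own sum the reference, and no order of precedence is stated.

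Several stronger readings are tempting, and the documents do not support them:

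- **That PR definitely excludes metastases.** The PR line does not say so. Its parenthesis may be a loose gloss on target lesions, which 8.1.2 defines without limit by site, and the literal reading fits poorly with a population that includes metastatic disease. What stands is that the text permits that reading and conflicts with its neighbors.
- **That longest diameter is the wrong axis for nodes.** Qualifying on one axis and summing on another is not in itself a contradiction, and 8.1.2 and 8.1.3 use longest diameter consistently. Section 5.1 requires a node to be serially measurable according to RECIST 1.1; it does not spell out serial short-axis measurement. Calling either axis correct needs the content of a guideline that is cited but not reproduced.
- **That true responders will be lost.** The examples show errors in both directions, so a table of lost power alone would mislead.
- **That the trial is underpowered.** The sample size calculation is correct. Every loss shown above depends on an assumed rate.

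**Conclusion.** The point holds as a defect in the definition of the primary endpoint. The conflict over the lesion set is in the current text: the PR line does not match 8.1.2, the progression line or the enrolled population. The axis question is a lesser gap: nodes qualify on one dimension and are summed on another, with an unranked reference to RECIST 1.1 beside both.

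The size is unknown. At the illustrative rates, 10% of responders missed costs about 7 points of power (0.801 to 0.730), and 2% of non-responders scored PR takes type I error from 0.047 to 0.118, more than double. These figures assume that misclassification is independent between patients and occurs at the same rate in both stages. They show how sensitive a rule of four in 29 is; they do not forecast what would happen. The design figures in 10.1 stand unchanged.

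**What to change.** 1. In 8.1.3, delete the parenthesis in the PR line, so that PR and progression use the same sum over all target lesions.
2. In 8.1.2, state one axis rule for nodal targets, consistent with how they qualify in 5.1 and 8.1.1 and checked against the RECIST 1.1 guideline cited in 10.2. Apply it at baseline and every later visit, and align the wording of the sum in 8.1.3.
3. Give the RECIST version in 8.1.3 and state that RECIST 1.1 governs wherever the written-out text differs.

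The cost is wording only: no extra scans, readers or patients, and no change to the 10/29 design. If any responses have already been scored, re-score them under the single rule.
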